## **9.3 Explorative Efficacy Analysis**

### **9.3.1 Landmark Analyses**

To explore the effect of the single-agent maintenance treatment on PFS a landmark analysis will be performed based on the primary endpoint definition. The landmark will be set to the start of the maintenance therapy. Only ITT patient still at risk for progression and death at this time point will be used for the analysis. The landmark PFS will be calculated from the start of maintenance treatment using the PFSp definition accordingly. Cox regression model will be applied including the treatment effect and the stratification factors. Kaplan-Meier analyzes will be presented.

Corresponding landmark analyses will be presented for OS.

### **9.3.3 Correlation of Pharmacokinetic Parameters with PFS and CBR**

The following PK parameters of CetuGEX™ serum concentrations will be investigated concerning their impact on efficacy outcomes in the subgroup of patients who were treated with CetuGEX™

- Trough levels after 1st, 2nd and 3rd infusion (= pre-infusion concentrations at 2nd, 3rd and 4th infusion)
- Post-infusion concentration after 1st, 2nd and 3rd infusion.

Cox regression models including the PK parameter as continuous covariable will be fit to the primary PFS endpoint. Separate analyses will be performed for each of the 6 PK parameters. Hazard ratios, the corresponding 95%-confidence intervals and the p-values of the Wald test will be presented. A forest-plot will be provided to illustrate the hazard ratios and confidence interval for all 6 PK parameters in one figure.

Logistic regression models including the PK parameters as continuous covariable will be fitted to the CBR as assessed by the central review (RECIST). Separate analyses will be performed for each of the 6 PK parameters. Odds ratios, the corresponding 95%-confidence intervals and the p-values of the Wald test will be presented. Moreover, sample statistics of the PK parameters grouped by CB response (yes/no) will be presented including p-values of the Wilcoxon rank test. A forest-plot will be provided to illustrate the odd ratios and confidence interval for all 6 PK parameters in one figure.

These analyses will be based on PK population.

## **10. SAFETY AND TOLERABILITY ANALYSES**

The safety analysis will be performed for the SAF population.

The analysis of safety assessments in this study will include summaries of the following categories of safety and tolerability data:

- AEs (including IRRs)
- Clinical laboratory investigations (biochemistry, hematology, urinalysis)
- Vital signs
- ECG investigations
- ECOG performance status

Findings in post-baseline physical examinations will be documented as AE and analyzed as part of the general AE analysis.

### **10.1 Adverse Events**

Adverse Events will be coded using MedDRA version 16 or newer.

An AE is defined as treatment emergent (TEAE), if the first onset or worsening is at or after the first administration of IMP (CetuGEXTM or cetuximab) and within 28 days after last administration.

If the start date or time of an AE is partially or completely missing, the AE will be assumed to be treatment-emergent if it cannot be definitely shown that the AE did not occur or worsen during the treatment emergent period (worst case approach). Missing dates and times will not be replaced for display in listings and further calculations.

Thus, the following approach will be taken:

- If the start time of an AE is missing, but the start date is complete, an AE will only be excluded from treatment-emergent AEs if the start day is before day of first treatment or the start day is after end day of the treatment-emergent period.
- If the start time and day are missing but the start month is complete, an AE will only be excluded from treatment emergent AEs if the start month is before month of first treatment or the start month is after end month of treatment-emergent period or if the stop date/time information is sufficient to show the event ended before the start of treatment.
- If the start day and months are missing but the start year is complete, an AE will only be excluded from treatment-emergent AEs if the start year is before year of first treatment or if the start year is after end year of treatment-emergent period or if the stop date/time information is sufficient to show the event ended before the start of treatment.
- If start date is completely missing, an AE will not be excluded from treatment-emergent AEs unless the stop date/time information is sufficient to show the event ended before the start of treatment.

Time from first treatment to onset of AEs [days] and duration of AEs [days] will be calculated for complete dates only and will be included in listings.

In the following infusion related reactions (IRRs) are defined as AE marked as infusion related reactions (IRRs) by the investigator and/or specific AEs which occurred at or the day after an infusion. The relevant AEs will be identified as a list of Preferred Terms which will be compiled before data base lock.

An AE summary table will be presented including rows with the number of patients with

- AEs
- TEAEs
- SAEs
- Any Deaths (NCI CTCAE V4.0 Grade 5 TEAEs and/or with an outcome of death)
- NCI CTCAE Grade 4, 3, 2, 1 TEAEs
- Adverse drug reactions (ADRs) (related or possibly related TEAEs)
- TEAEs leading to withdrawal of study treatment

- TEAEs leading to drug interruption or infusion rate reduction
- TEAEs requiring additional medication
- TEAEs constituting IRRs
- TEAEs marked as disease related symptoms

Incidences of TEAEs will be presented for all TEAEs and separately for the combination treatment (TEAE which occurred before first maintenance treatment) and maintenance treatment (TEAE which occurred at or after first maintenance treatment).

Incidences of TEAEs will be calculated on Preferred Term level, on System Organ Class level (SOC) and globally by treatment group. On each analysis level, a patient will be counted only once. Summaries of incidence rates (frequencies and percentages) of individual TEAEs by MedDRA SOC and Preferred Term will be prepared. Such summaries will be displayed for all TEAEs, TEAEs by maximum severity graded according to NCI-CTCAE (Version 4.03), TEAEs by strongest relationship to study treatment, and TEAEs by strongest relationship to chemotherapy. In the SOC/PT tables, events with missing grade or relationship information will be classified into the worst category. No statistical tests will be performed. In addition, separate summaries of incidence rates of IRRs and all TEAEs without IRRs by SOC and PT will be given.

IRRs will be linked to the last infusion administered before the occurrence of the IRR. Incidence rates will be calculated by SOC and PT on a per infusion basis. Moreover the first infusion per patient with a least one IRR will be identified and summarized in frequency tables.

Also, a summary of incidence rates of TEAEs by SOC and PT and of incidence rates of IRRs by FcγRIIIa-allotype subgroups (FF, FV and VV), by FcγRIIa allotypes (HH, HR, RR) the occurrence of ADAs (no/yes) and the CetuGEX™ concentration ( $C_{max}$ ) after the 3rd infusion ( $\leq$  median/ $>$ median) will be prepared.

In the AE listings all recorded AEs will be included, TEAEs will be identified by a flag variable.

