10.2 Study Duration

The overall study duration is expected to be approximately 48 months (including 24 months of active enrollment, a treatment phase until the respective number of PFS events is reached of approximately 12 months after the date of randomization and ongoing follow-up for overall survival for 24 months after randomization of the last patient).

The sequence and maximum duration of the study periods and treatment for each patient will be as follows:

- Screening: to be performed within 28 days prior to randomization to assess general eligibility for this study.
- Combination treatment phase: maximum of 6 treatment cycles of combination treatment.
- Single-agent maintenance phase: until disease progression.
- Follow-up: at least 24 months after the date of randomization of the last patient.

All patients will be treated until disease progression, unacceptable toxicity or any other withdrawal criterion is met.

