### **5. SAMPLE SIZE DETERMINATION**

Approximately 240 patients will be randomized in this study.

The log-rank test will be used to test the hypothesis that patients assigned to the CetuGEX™ arm have increased PFS compared to patients assigned to the control arm.

The sample size calculation is based on the following assumptions:

- The median PFS in the control arm is expected to be 5.6 months post randomization.
- It is expected that the median PFS in the CetuGEX™ arm can be increased to 8.4 months corresponding to a hazard ratio of 0.67.
- The overall trial duration will be approximately 36 months with an anticipated recruitment time of 24 months, anticipated treatment phase until PFS events are reached of approximately 12 months after randomization of the last patient (data

cut-off for main analysis) and ongoing follow-up for overall survival for at least 24 months after randomization of the last patient.

- Drop-outs are expected to occur at times following an exponential distribution and resulting in a drop-out rate of 10% at the cut-off for PFS analysis.
- Patients will be randomized in a 1:1 ratio.
- The overall two-sided significance level will be 0.05 and the power to be maintained 80%.

Based on these assumptions, approximately 240 patients have to be randomized to observe the required overall number of 192 events.

If the required number of events is not reached as planned after 12 months from last patient randomized, the main analysis will be postponed to obtain more events but not more than additional 6 months.

Assuming a corresponding effect on OS (hazard ratio 0.67) and a median overall survival of 10.6 months in the control group the number of survival events to be observed after a 24-months follow-up for survival will be 183.

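### Outside the special-interest and infusion-reaction analyses, TEAEs and SAEs have no exposure-adjusted summary, although the design implies longer time at risk on CetuGEX

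*SAP*

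**What the plan says.** Protocol 10.2 sets the length of treatment: "All patients will be treated until disease progression, unacceptable toxicity or any other withdrawal criterion is met". Under SAP 10.1 the treatment-emergent window opens at the first antibody dose and closes 28 days after the last. SAP 4.2 has the safety analysis run at the data cut-off and include patients still on treatment.

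SAP 5 gives the expected PFS by arm: "The median PFS in the control arm is expected to be 5.6 months post randomization" and "It is expected that the median PFS in the CetuGEX™ arm can be increased to 8.4 months corresponding to a hazard ratio of 0.67".

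For the general tables (all TEAEs, maximum grade, relationship, withdrawal, SAEs), SAP 10.1 to 10.1.2 specify counts and percentages of patients, with the rule "On each analysis level, a patient will be counted only once". SAP 7.1 makes all patients of the arm's population the default denominator, and 10.1 names no other. SAP 8.4 summarises treatment duration but does not link it to adverse events.

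Three provisions go further:
- SAP 10.1 tabulates TEAEs separately for the combination and maintenance phases.
- SAP 10.1 gives infusion-related reactions per infusion as well.
- SAP 10.1.3 analyses time to first occurrence by Kaplan-Meier for seven groups of special interest: neutropenia, liver enzyme increases and hypomagnesemia at grade 3 or higher, the skin and gastrointestinal organ classes, mucositis and conjunctivitis.

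**The concern.** A patient percentage rises with time at risk. If one arm is treated and observed for longer because progression comes later, it collects more patients with an event even when the monthly risk is the same. Comparing safety between arms is a secondary objective, and the general tables are what a reader will use for it. If CetuGEX achieves the PFS gain the trial is designed to detect, those tables would make it look more toxic than it is for any event that keeps accruing. Any SAE, any grade 3 or higher TEAE and TEAEs leading to withdrawal have no analysis that would correct this.

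**Working it through.** **1. The plan's own figure.** Inputs from SAP 5: medians 5.6 and 8.4 months (HR 5.6/8.4 = 0.667), two-sided 0.05, 80% power, 1:1 allocation. Schoenfeld: 4 × (1.960 + 0.842)² / (ln 0.667)² = 191 events, and 192 events give 80.2% power. With exponential PFS, uniform accrual over 24 months, 12 further months, and drop-out "resulting in a drop-out rate of 10% at the cut-off for PFS analysis", 192 events need 238 patients. The SAP says "approximately 240 patients have to be randomized to observe the required overall number of 192 events", so the exponential model used below reproduces the design.

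**2. Time on treatment.** Progression hazard μ = ln 2 / median: 0.1238 per month (cetuximab) and 0.0825 (CetuGEX). The ratio of medians is 1.50. Potential follow-up U at cut-off is uniform on 12 to 36 months. Averaging (1 − e^(−μU))/μ over U gives mean time on treatment of 7.5 and 10.2 months, a ratio of 1.36. Stopping for reasons other than progression, at an assumed equal hazard of 0.02 to 0.10 per month, lowers the ratio further; without the cut-off it takes 1.50 down to 1.40 to 1.23.

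**3. All-TEAE table at identical monthly toxicity.** The documents give no monthly event rate, so the hazard λ is an assumption and is shown as a range. With treatment duration D exponential and w = 28/30.4375 = 0.92 months, incidence = 1 − E[exp(−λ × min(D + w, U))].

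| λ per month | Cetuximab | CetuGEX | Gap (points) |
|---|---|---|---|
| 0.02 | 14.7% | 18.7% | 4.0 |
| 0.05 | 31.0% | 38.0% | 7.0 |
| 0.10 | 48.9% | 57.3% | 8.4 |

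Without the cut-off the formula reduces to 1 − e^(−λw) × μ/(μ + λ), which can be checked by hand. At λ = 0.05 it gives 32.0% against 40.5%.

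**4. Combination phase.** Six three-week cycles last T = 126/30.4375 = 4.14 months. Mean exposure within T is (1 − e^(−μT))/μ = 3.24 and 3.51 months, a difference of 8%. Incidence λ/(λ + μ) × (1 − e^(−(λ+μ)T)), without the 28-day window, differs by 0.5, 1.2 and 2.1 points for the three hazards. For events confined to the first three weeks the gap is 0.2 to 0.6 points (hazards 0.2 to 1.0 per month).

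**5. Maintenance phase.** Assume maintenance starts at week 18. The share still progression-free is e^(−μT) = 59.9% and 71.1%. With all patients of the arm as denominator, incidence = e^(−μT) × {1 − E[exp(−λ × min(R + w, U − T))]}, where R is exponential with hazard μ.

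| λ per month | Cetuximab | CetuGEX | Gap (points) | Ratio |
|---|---|---|---|---|
| 0.02 | 8.4% | 12.4% | 4.0 | 1.47 |
| 0.05 | 18.0% | 25.7% | 7.7 | 1.43 |
| 0.10 | 28.7% | 39.5% | 10.8 | 1.38 |

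Dividing by the share entering (0.599 and 0.711) gives percentages of those who started maintenance: 14.1% against 17.5%, 30.0% against 36.2%, and 48.0% against 55.6%. Correcting the denominator alone therefore leaves a gap of about 3 to 8 points.

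**6. Would one pooled rate repair it?** Take front-loaded toxicity, identical in both arms: hazard 0.10 per month to week 18 and 0.01 afterwards (assumed), with the cut-off but not the 28-day window. Crude incidence is 29.6% against 33.1%. First events per 100 patient-months over the whole study are 5.54 against 4.74, so CetuGEX looks roughly 15% safer at identical hazards. Rates taken separately by phase return 10 and 1 per 100 patient-months in both arms.

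**The case against.** The strongest reply is that the SAP already covers much of this. The special-interest groups include two whole organ classes and are analysed as time to first event. Infusion-related reactions have an exposure denominator. The phase split nearly balances exposure where chemotherapy toxicity arises. The organ-class and preferred-term tables are descriptive and untested, and treatment duration is reported by arm, so a careful reader can see an imbalance. All of this stands. It confines the point to events outside those analyses, and mainly to the pooled and maintenance tables.

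Three stronger readings are tempting, and the documents do not support them:
- A reader might infer that adverse events are compared only as crude percentages. SAP 10.1 and 10.1.3 show otherwise.
- A reader might infer that the plan expects 50% longer treatment. The plan states PFS medians, not treatment duration. The 1.50 is an upper value, because the cut-off and stopping for other reasons reduce it.
- A reader might infer that crude percentages would flatter CetuGEX if it failed. With equal PFS the exposure is equal and there is no such distortion; it would arise only if treatment were shorter on CetuGEX.

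The reply is also right that a pooled whole-study rate could mislead in the other direction (step 6). That limits which remedy is acceptable but does not remove the gap.

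**Conclusion.** The point holds as a minor improvement in reporting. The sizes rest on exponential PFS at the planned medians, treatment stopping only at progression or cut-off, and a constant, equal event hazard in the range shown. Stopping for toxicity would shrink them, as would a smaller PFS effect than planned. The inference that every safety table is distorted would go too far, since combination-phase and early-onset events are nearly unaffected. The rates should be specified before results are known, because the direction of the distortion depends on the PFS result and rates added afterwards could look selective.

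**What to change.** In SAP 10.1, keep the crude percentages and add:

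1. In Tables 14.3.1.2.2 and 14.3.1.2.3, patients with a first event per 100 patient-months at risk, separately for the combination and maintenance phases. Time runs from the start of the phase to the first event in that phase, or to the end of its at-risk window. State that the maintenance denominator is patients who entered maintenance.
2. The time-to-first-event method of SAP 10.1.3 for any SAE, any grade 3 or higher TEAE, and TEAEs leading to withdrawal. Since SAP 4.2 includes patients still on treatment, state that those without a Safety Visit are censored at the data cut-off.
3. A sentence saying that no single pooled whole-study rate will be used to compare the arms.

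The cost is a few table columns and three sets of curves, built from dose and onset dates already collected. The rates assume a roughly constant hazard within each phase; the curves do not.

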11.2.2 Evaluation

11.2.2.1 Severity of Adverse Events

The clinical severity of an AE will be graded using the NCI CTCAE v4.0 (<http://ctep.cancer.gov/reporting/ctc.html>). For those AEs not listed in the CTCAE, the following grading system should be employed:

- | | |
|---------------------------|--|
| Mild (CTCAE grade 1): | Transient symptoms, awareness of sign/symptom, but easily tolerated and no interference with patient’s daily activities. |
| Moderate (CTCAE grade 2): | Marked signs/symptoms that interfere with patient’s usual activities, but still acceptable. |

Severe (CTCAE grade 3)	Incapacitating signs/symptoms, which cause considerable interference with the patient's daily activities, unacceptable.
Life-threatening (CTCAE grade 4)	Life-threatening or disabling adverse event.
Death (CTCAE grade 5)	Death-related adverse event. See CTCAE Guidelines for assigning grade 5

It is important to distinguish between severe AEs and SAEs. Severity is a classification of intensity whereas an SAE is an AE that meets serious criteria, as described in Section 11.1.4.

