11.2.2.4 Outcome at the Time of Last Observation

The outcome at the time of last observation will be classified as

- Recovered/resolved
- Recovered/resolved with sequelae
- Recovering/resolving
- Not recovered/not resolved
- Death*
- Unknown

*Although “death” is usually an event outcome, events such as sudden death or unexplained death should also be reported as SAEs.

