14.2.17.3	ITT, PP	Clinical Benefit Rate (Investigator Assessment) and p16 Status Logistic Regression Model	16.2.6.1
14.2.17.4	ITT, PP	Clinical Benefit Rate (Investigator Assessment) in p16 Status Subgroups Frequencies and Confidence Intervals	16.2.6.3
14.2.17.5	ITT, PP	Clinical Benefit Rate (Investigator Assessment) and EGFR Intensity Logistic Regression Model	16.2.6.1
14.2.17.6	ITT, PP	Clinical Benefit Rate (Investigator Assessment) in EGRF Intensity Subgroups Frequencies and Confidence Intervals	16.2.6.3
14.2.17.7	ITT, PP	Clinical Benefit Rate (Investigator Assessment) and EGFR Stained Cancer cells Logistic Regression Model	16.2.6.1

Table Number	Population	Table Title / Summary	Supporting Listing
14.3 SAFETY DATA			
14.3.1.1.1	Safety	Adverse Events Summary Table	16.2.7

Table Number	Population	Table Title / Summary	Supporting Listing
14.3.1.2.1	Safety	Treatment Emergent Adverse Events – All TEAE Incidences by SOC and Preferred Term	16.2.7
14.3.1.2.2	Safety	Treatment Emergent Adverse Events – During Combination Treatment Incidences by SOC and Preferred Term	16.2.7
14.3.1.2.3	Safety	Treatment Emergent Adverse Events – During Maintenance Treatment Incidences by SOC and Preferred Term	16.2.7
14.3.1.3.1	Safety	Treatment Emergent Adverse Events by Maximum CTC Grade – All TEAE Incidences by SOC and Preferred Term	16.2.7
14.3.1.3.2	Safety	Treatment Emergent Adverse Events by Maximum CTC Grade – During Combination Treatment Incidences by SOC and Preferred Term	16.2.7
14.3.1.3.3	Safety	Treatment Emergent Adverse Events by Maximum CTC Grade – During Maintenance Treatment Incidences by SOC and Preferred Term	16.2.7
14.3.1.4.1	Safety	Treatment Emergent Adverse Events by Strongest Relationship to Study Drug – All TEAE Incidences by SOC and Preferred Term	16.2.7
14.3.1.4.2	Safety	Treatment Emergent Adverse Events by Strongest Relationship to Study Drug – During Combination Treatment Incidences by SOC and Preferred Term	16.2.7

Table Number	Population	Table Title / Summary	Supporting Listing
14.3.1.4.3	Safety	Treatment Emergent Adverse Events by Strongest Relationship to Study Drug – During Maintenance Treatment Incidences by SOC and Preferred Term	16.2.7
14.3.1.5.1	Safety	Infusion-Related Reactions Incidences by SOC and Preferred Term	16.2.7
14.3.1.5.3	Safety	Infusion-Related Reactions Incidences by SOC and Preferred Term on a Per Infusion Basis	16.2.7

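### The SAP's rule for ungraded adverse events does not exclude Grade 5, so read literally it would tabulate a non-fatal event as a death

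*SAP*

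**What the plan says.** SAP section 10.1 plans SOC/PT summaries that include "TEAEs by maximum severity graded according to NCI-CTCAE (Version 4.03"). For gaps in the data it then states that, in the SOC/PT tables, "events with missing grade or relationship information will be classified into the worst category". It does not name the worst category for grade.

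The affected outputs are in SAP section 15.1. They begin with Table 14.3.1.3.1, "Treatment Emergent Adverse Events by Maximum CTC Grade – All TEAE", and continue with 14.3.1.3.2 (combination treatment) and 14.3.1.3.3 (maintenance).

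Section 10.1 also plans an AE summary table (Table 14.3.1.1.1). One row is "Any Deaths (NCI CTCAE V4.0 Grade 5 TEAEs and/or with an outcome of death"), and Grades 4 to 1 are listed in a separate row entry. The missing-grade rule is stated for the SOC/PT tables and not for this one.

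**The concern.** A worst-case rule is meant to avoid understating toxicity when information is missing. It works for relationship, where the worst value is simply related. Grade is different, because the top of the scale is not a more intense version of the same event but the patient's death. Whether the patient died of the event is recorded separately, so the rule could overwrite something the database already knows.

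What is at stake is the reading of the safety tables. Fatal events by preferred term are among the first things a reader compares between a new antibody and cetuximab. SAP section 10.1 plans no tests on these incidences, so the displayed counts carry the message. SAP section 1 allows the planned analyses to be used in study reports, regulatory submissions and manuscripts.

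**Working it through.** There is no planned figure to reproduce. The check sets the rule beside the scale, the outcome item and the summary table.

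**1. The scale.** Protocol section 11.2.2.1 grades by CTCAE. It adds a fallback list for events that CTCAE does not cover, with each level labelled by its CTCAE grade. The top two levels are "Life-threatening (CTCAE grade 4") and "Death (CTCAE grade 5"). The SAP also treats Grade 5 as death, since a Grade 5 event alone places a patient in the Any Deaths row. The worst category on this scale is therefore Grade 5.

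**2. Any limit on the rule.** SAP section 7.1 rules out further imputation of missing values unless a relevant section specifies it. The sentence in section 10.1 is the only one that deals with missing grade, and it contains no cap.

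**3. What else is known about the event.** Protocol section 11.2.2.4 makes outcome a separate item ("The outcome at the time of last observation will be classified as"), with categories that include recovery and death. Protocol section 11.2.3 lists severity and outcome as separate entries. A missing grade does not make the outcome unknown.

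**4. The rule applied to cases.**

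| Recorded outcome | Recorded grade | Grade in the SOC/PT tables, literal rule | Any Deaths row, rule not extended | Any Deaths row, rule extended |
|---|---|---|---|---|
| Death | missing | 5 | counted, by outcome | counted |
| Recovered | missing | 5 | not counted | counted |
| Recovered | 2 | 2 | not counted | not counted |

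The second line is the defect. If the rule stays confined to the SOC/PT tables, they can show more Grade 5 patients than the summary table shows deaths. If it is carried over, the tables agree but the Any Deaths row is inflated.

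**5. Size per patient.** SAP section 10.1 counts a patient once on each analysis level. Suppose one patient has k ungraded non-fatal events in p distinct PTs and s distinct SOCs, so that s ≤ p ≤ k. In one table the false Grade 5 entries are at most p across PT rows, s across SOC rows and 1 overall.

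- k = 2 events, same PT: at most 1, 1 and 1.
- k = 2 events, different PTs, same SOC: at most 2, 1 and 1.

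These are upper bounds, because a patient already at a true Grade 5 in a row adds nothing there. An event in the all-TEAE table also appears in the combination or the maintenance table.

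**6. Number of patients.** The documents give neither an expected number of events nor a proportion without a grade, so no total follows.

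**7. The SAP's own precedent.** For missing AE start dates, section 10.1 also takes a worst-case approach, but gives way when the stop date shows that the event ended before treatment began. The grade rule has no matching check against outcome.

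**The case against.** The strongest reply is that the SAP never says Grade 5. The summary table separates deaths from Grades 4 to 1, so the author may have meant the worst non-fatal grade. That is possible, but the text does not say it, and a programmer working from the sentence and the scale could reasonably code Grade 5. The wording needs settling on either reading.

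The second reply is that missing grades should be rare. Protocol section 10.3.6.3 requires the investigator to assess and document severity. Section 14.4.2 provides consistency checks and makes sites responsible for resolving queries. SAP section 8.2 adds a data review meeting before lock. This stands, and it is the main reason the point is minor. It does not remove the point: the SAP foresaw missing grades, and under SAP section 4.2 the main safety analysis uses all available data, including patients still on treatment.

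The third reply is that a false Grade 5 would be exposed elsewhere, by SAE reconciliation, the SAE tables and case listings, and the full AE listing. This also stands, but it means the report would contain a discrepancy that someone has to explain.

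A reader might infer that the plan will inflate or even double the trial's count of fatal events. The documents do not support that. Any such figure needs assumed numbers of events, ungraded events and true deaths, none of which they give. It would also compare events with patients, although the tables count each patient once per level. Under the rule's stated scope, the Any Deaths row is not changed at all.

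**Conclusion.** The rule is wrong as written, with minor severity. Taken literally, it turns an ungraded non-fatal event into a Grade 5 entry in Tables 14.3.1.3.1 to 14.3.1.3.3, even against a recorded outcome other than death, and can set those tables against the summary table. The bound is one false entry per affected patient in any PT row, any SOC row and the overall row of a table. The total cannot be derived and is zero if all grades are complete at lock.

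The conclusion rests on two conditions: that the worst category is read as the top of the CTCAE scale, and that some grades are still missing when the tables are run. The defect lies in safety reporting only. It does not reach PFS or OS, which take no input from AE grade. The relationship half of the sentence is an ordinary conservative convention and is not at fault.

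**What to change.** Replace the grade part of the sentence in SAP section 10.1 with a rule to this effect: a missing grade is set to Grade 5 only if the recorded outcome of that event is death; otherwise it is set to Grade 4, the worst non-fatal category, or shown in a separate category for missing grade. The SAP should choose one of the two, footnote imputed grades, and state whether the rule also covers the AE summary table. Worst-case handling of missing relationship should stay.

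A default of Grade 3 for events not flagged as life-threatening would not be a sound substitute. The Grade 4 level in Protocol section 11.2.2.1 also covers disabling events, so that default could under-grade. Protocol section 11.2.3 names only hospitalization and death beside the seriousness item, so a life-threatening flag for every event cannot be assumed.

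The cost is one SAP sentence, one programming condition and a footnote. No new data are needed, because outcome is already collected.
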